Figures B6-B7 shows Bayes estimates for p_1 , p_2 , and $p_1 - p_2$. The average credibility intervals for p_1 and p_2 are somewhat wider than corresponding confidence intervals. The reason for this is unclear. Although the treatment effect is an odds ratio. i.e., $p_2(1 - p_1)/[p_1(1 - p_2)]$ in both approaches, an attractive aspect of the Bayes MCMC method is that it is easy to get the posterior distribution of the simple treatment difference, as shown $p_2 - p_1$ in Figure B7. The credibility interval for $p_1 - p_2$ seems less sensitive to ICC than other interval estimates investigated.

[figure not shown]
18.1 Figure B5: Bayes power; Alternative Cases

18.2 Figure B6: Bayes Credibility Intervals for P1, P2; Alternative Cases

[figure not shown]

18.3 Figure B7: Bayes Credibility Intervals for P1-P2; Alternative Cases

[figure not shown]

Figures B8-B10 give test size and credibility intervals under the “Null” scenarios of Table 4. Figures B8-B9 are comparable to their Frequentist analogues (Figure 4-5, sections 11.8.3-11.8.4) As in figure B7, the credibility interval for $p_2 - p_1$ (Figure B10) seems less sensitive to ICC than other interval estimates investigated.

[figure not shown]
18.4 Figure B8: Bayes Test Size; Null Cases

18.5 Figure B9: Bayes Credibility Intervals for P1, P2; Null Cases

18.6 Figure B10: Bayes Credibility Intervals P1-P2; Null Cases

We document here the SAS code for the Bayesian approach, which employs the Markov Chain Monte Carlo method.

```
Proc mcmc data = simmsimul nbi = 1000 nmc = 10000 thin = 2 see = 159
  monitor - (beta0-beta2 beta2_gt_0 p1 p2 pdiff) statistics = (summary intervals);
  parms beta0-beta2 0;
  parms sigma2 1;
  prior beta0-beta2~normal(mean = 0, var = 1000);
  prior sigma2~ igamma(shape = 0.001, scale = 0.001)
  random b0 ~normal(mean = 0, var = sigma2) subject = site;
  array p[2]
  p[treat+1] = logistic(beta0 + beta1 * 22 + beta2 * treat);
  pdiff = p2 - p1
  eta = beta0 + beta1 * month + beta2 * treat + b0;
  pi = logistic(eta)
  model z ~binomial(n = trials, p = pi);
  beta2_gt_0 = beta2 > 0;
run;
```

[figure not shown]
Revised SAP

Analytic Model Adjustments

This section provides a description of adjustments to the computational model used in the planned analyses that were necessary to ensure the validity of the performed tests of statistical significance of the hypothesized effects. In general, two updates were implemented: (1) exclusion of time in the model; and (2) the method of adjusting for site.

Time. The proposed analytical plan in the SAP document included a fixed effect for the evaluation period (Baseline vs IF evaluation, called “arm” in the SAP), fixed linear effect of time (days from the study start to the date of enrollment of each patient in the observational cohorts study, a continuous variable called “time”) and a random effect for site (called “site”). Such a model is appropriate for analyzing data collected in a fully implemented multisite stepped-wedge study design. An important characteristic of a stepped-wedge study design is a substantial overlap of control and treatment periods. (Figure 1)

FIGURE 1. Characteristic of a Stepped-Wedge Study Design: Substantial Overlap of Control and Treatment Periods

In such a design, the effect of time can be analytically partially disentangled from the treatment effect. However, the CTN0069 study was not implemented as a modified stepped-wedge design as initially described. As implemented, in CTN-0069, there was virtually no overlap between the baseline evaluation and IF evaluation periods.

Evaluation of the distributional properties of the time variable data indicated that this variable, originally included as one of the explanatory factors in the analytical model, overlaps 96% with the intervention/treatment factor in the study. Including two highly overlapping variables in the analytical model can create a computational, statistical, and mathematical error. Collinearity, or high association between two explanatory variables means that the collinear variables contain the same information about the dependent variable, and that these only nominally different measures actually quantify the same

phenomenon or information. In CTN-0069, the variables “time” and “arm” are highly redundant. The best and most statistically robust analytical models are called “low noise” models in which the predictor variables each correlate highly with the outcome variable but correlate with each other at most only minimally. Collinearity and redundancy may lead to a failure to reject a false null hypothesis of no intervention effect. Consequently, the “time” variable was removed from the adjusted computational model.

Site. Additionally, the four geographically diverse study sites were purposefully selected to represent different clinical contexts and different patient populations. Conceptually, these EDs cannot be considered as a random sample of all EDs in the US, and probabilistically, no four values selected from a large population can be considered to represent randomness, even if they are drawn by chance. Consequently, site was included in the primary analytic models as a fixed effect, and not a random one in order to provide additional information on between site differences. The study results demonstrated not only statistical difference effects between the sites, but also substantial, large, important, and informative site differences.

Thus, the final analytic model for both the primary implementation and effectiveness outcomes was a logistic regression model with fixed effects for site and evaluation period.

Site Differences for Primary Effectiveness Outcome

As noted in the manuscript, there were substantial site differences with respect to the primary effectiveness outcome. Three of the four sites was associated with an increase in treatment engagement during the IF evaluation period, however for one site there was a decrease. To explore this further, a logistic regression model was fit assessing the site-by-evaluation period interaction. In this model, there was a statistically significant interaction ($p=0.021$) indicating that the differences observed across sites was statistically significant. Future work could explore these relationships further, including evaluation of differences in site characteristics that may explain the observed qualitative interaction.

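### The Revised SAP removes calendar time from both primary models for reasons that the SAP's own dates and the protocol do not support, leaving a before-after contrast that absorbs any secular trend

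*SAP*

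**What the plan says.** Protocol 12.14.1 models the logit of success as evaluation period plus linear calendar time plus a random site intercept, tested one-sided at 0.05. SAP 7.2 and 7.4 keep this model for the implementation and effectiveness outcomes.

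In the Revised SAP, placed after the Bayesian appendix, the time "variable was removed from the adjusted computational model", and the model for both outcomes becomes "a logistic regression model with fixed effects for site and evaluation period". It presents the change as "necessary to ensure the validity of the performed tests of statistical significance of the hypothesized effects" and gives four grounds:

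- Implementation: the "study was not implemented as a modified stepped-wedge design as initially described".
- Overlap: "there was virtually no overlap between the baseline evaluation and IF evaluation periods", and time "overlaps 96% with the intervention/treatment factor in the study".
- Computation: two such variables in one model "can create a computational, statistical, and mathematical error".
- Power: "Collinearity and redundancy may lead to a failure to reject a false null hypothesis of no intervention effect".

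The addendum cites the study results and the manuscript, so it was written with results in hand. It has no entry in the SAP 14.0 log, which ends at version 2.0, approved 20 September 2021. That version came 351 days after the last enrolment date (4 October 2020), names the last day of overlap (SAP 7.2.1), and still keeps time in the model.

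**The concern.** Period and calendar time are closely linked here because every site moves in one direction. The time term is the only part of the model that separates facilitation from whatever else changed. Without it, the period coefficient is a site-adjusted before-after difference.

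The protocol gives reason to expect change. Section 3.4 refers to national and state policy momentum toward medication treatment, and section 5.1 counts on a short study to limit time trends. COVID could act in either direction.

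Removing a pre-specified confounder after results are known, partly because it costs power, affects both primary conclusions. It would need a sound reason, so the stated reasons have to be checked.

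**Working it through.** **1. Was the design implemented as described?** Inputs: the SAP 3.3.6 dates, and the protocol 5.1 plan of 12-month baseline, 6-month IF and 12-month IF evaluation in 3-month steps. Day 0 is 10 April 2017.

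| Site | Baseline (days) | Baseline length | Gap | IF evaluation (days) | Net length |
|---|---|---|---|---|---|
| MA | 0-364 | 365 | 182 | 547-911 | 365 |
| NY | 87-451 | 365 | 182 | 634-1000 | 367 |
| OV | 182-546 | 365 | 181 | 728-1183 | 367 |
| PNW | 267-631 | 365 | 181 | 813-1273 | 366 |

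Net length excludes the COVID pauses. The plan implies one overlapping pair (site 1 IF evaluation, months 18-30; site 4 baseline, months 9-21), for 3 months. The dates give one pair (MA and PNW), days 547-631, or 85 days. The pauses came over a year later and did not affect it. Footnote 1 to protocol 12.6 says a late site 1 IF onset would make confounding complete; MA's IF evaluation opened on schedule.

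**2. Is collinearity worse than designed?** Assume 120 patients per site-period, evenly spread; VIF = 1/(1 − r²).

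| | Implemented | Planned |
|---|---|---|
| Overall r (VIF) | 0.87 (4.2) | 0.88 (4.5) |
| Within-site r (VIF) | 0.93 (7.1) | 0.93 (7.8) |
| Patients in overlap | 2 × 120 × 85/365 = 56 (5.8%) | 2 × 120 × 3/12 = 60 (6.3%) |

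Actual counts are not given and enrolment was uneven (SAP 11.0). If the two overlapping site-periods enrolled 50-140 each of 960, the share is 2.4-6.8%. The same footnote already disclosed partial confounding, and the power simulations kept month in the model.

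**3. Can the pre-specified model be fitted, with the stated power?** Protocol 12.9.1 claims power above 0.8 for 5 vs 25% and 25 vs 50%, and lower power for the other two scenarios. Simulated power with time retained, at site SD 0.3/0.8 on the logit scale: 0.99/0.97, 0.93/0.90, 0.65/0.58 (25 vs 40%) and 0.50/0.47 (15 vs 25%). This matches the protocol's split. No fit returned a missing estimate or standard error in 54,000 data sets.

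**4. What does dropping time do?** Within-site period midpoints lie 547-578 days apart, about 18-19 months. A monthly odds ratio of 1.02 therefore gives a spurious IF odds ratio of about 1.02^18.3 = 1.44 (simulated 1.43-1.45); 0.98 gives about 0.69 (simulated 0.68-0.70).

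One-sided rejection with no IF effect, base rates 5/15/25%, site SD 0.3 and 0.8, ChangeToOne applied, z > 1.645. There were 1,500 replicates per case, except 500 in 8 of the 18 SD 0.8 null cases.

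| Trend | No time, fixed site | Fixed site + time | Random site + time (pre-specified) |
|---|---|---|---|
| Flat | 4-5% | 3-6% | 5-8% |
| OR 1.01/month | 16-36% | 3-6% | 5-8% |
| OR 1.02/month | 43-85% | 3-6% | 5-8% |
| OR 0.98/month | about 0% | 3-6% | 5-8% |
| Step, OR 1.5, Oct 2018 | 38-84% | 11-19% | 13-23% |
| Fall, OR 1.5, Mar 2020 | 3-5% | 7-11% | 8-13% |

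The 3-6% and 5-8% entries are ranges over the flat and linear cases together. A 3-df spline with fixed site gives 7-8% for the step and 4-5% for the fall (SD 0.3 only). Pre-COVID data with fixed site and time give 5-6% for the fall (SD 0.3). A second simulation on the planned layout, at annual OR 1.25, gives 18-78% without time; with linear time it is 4.3-5.9% over all trends tried.

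**5. Is the time scale consistent?** SAP 3.3.6 counts from each site's opening. On that clock baseline is days 0-364 and IF evaluation starts at 546-547, so the periods never overlap. The Revised SAP counts from study start. In the Table 15 shell, day 632 fits study start: 1 January 2019 is 631 days after 10 April 2017, or day 632 counting that date as day 1. Day 1423 does not fit. The COVID time point, 2 March 2020, is 1057 days after study start, while day 1423 falls in March 2021, after enrolment closed. The Bayesian code in SAP 7.2 evaluates time at 22, the protocol's month, although SAP time is in days.

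**The case against.** The overlap is thin: one site pair, 85 days, about 6% of patients. Calling it virtually absent is a fair description, and the undefined 96% could be the share of patients outside it, since the range above implies 93.2-97.6%. Weak separation of time from period is mainly a property of the design, so restoring time does not create strong concurrent control. These points stand.

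The planned layout used above is reconstructed from the text because the timeline figure is not shown. The footnote's 3-week example does not fit a 3-month overlap. SAP 2.3.3 describes random selection among sites still in baseline, which could be read as a different design. However, the dated switches about three months apart fit that description too.

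The pre-specified model is not ideal. It runs slightly above 5% with four random sites, handles steps imperfectly, and does worse than the no-time model for a fall in March 2020. The simulations used the study clock; on the literal site clock of SAP 3.3.6 the random-site standard error is about 10-17% larger (200 replicates per case). The study clock is what protocol 12.14.1, day 632 and the Revised SAP imply.

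The documents give no trend, and under a flat trend the no-time test keeps its level. The addendum states its change openly, and time-adjusted results may appear in the manuscript or the final study report; the documents do not say. None of this makes a no-time model the right primary analysis.

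**Conclusion.** The concern holds and must be fixed. The dates match the planned schedule, so the claim of departure from design is wrong as written. The overlap claim is overstated as a reason: the overlap was small by design and disclosed. The computational error is asserted, not shown. The last ground is lost power, which is no threat to the validity of a test.

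The final model's IF effect includes any secular trend, of unknown size and direction. A rise of 1-2% a month in the odds would lift the false-positive rate from 5% to somewhere between 16% and 85%; a 2% monthly fall could hide a real effect. These figures rest on even enrolment of 120 per site-period, the base rates and site SDs above, and assumed trends. The date arithmetic rests only on SAP 3.3.6.

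**What to change.** For both primary outcomes:

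1. Report the pre-specified time-adjusted model as the primary result. Show the fixed-site, no-time model beside it, labelled a post hoc before-after comparison that cannot be separated from secular trend.
2. Add two checks, a spline time term and fixed site plus linear time, and keep the pre-COVID analysis of SAP 7.5.2.
3. State that the time-adjusted estimate is imprecise, relies on a common linear slope carried across the 6-month gap, and does not fully handle step changes.
4. Withdraw the statements that the design was not implemented as described and that removal was needed for valid tests. Say that collinearity is high and as designed. Define or delete the 96%.
5. Use one origin and unit, days from study start, and reconcile SAP 3.3.6 with it. Correct day 1423 in the shells for Tables 15, 21, 24 and 29, and replace the fixed 22 in the Bayesian code with the stated evaluation days.
6. Enter the revision, with date and reason, in the SAP 14.0 log.

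Cost: addendum wording, code already in SAP 7.2, two extra model runs and corrected shells. Relative to no time, the standard error is 1.9-2.4 times larger with the pre-specified model, 2.2-2.6 with fixed site plus time, and 3.0-3.6 with fixed site plus spline. Power is low in the small-effect scenarios, as protocol 12.9.1 already accepts. The slight excess over 5% is of the kind protocol 12.8 calls tolerable.

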3.3.6 Calendar Time

Calendar time for analysis is defined as the number of days since the site opened for enrollment in the baseline evaluation period. Below are the start and end dates for each site in each evaluation period. The start date is defined as the date the site was given access to the eClinical system to begin enrolling participants in the study for that particular evaluation period. The end date is defined as the last day the site was able to enroll participants in the EDC system for each evaluation period. Note that during the IFEP, enrollment was paused due to the COVID-19 public health measures put into place at two sites, Harborview Medical Center and University of Cincinnati. The days enrollment was paused will be considered as part of the primary analysis and several sensitivity analyses will be performed to account for this pause.

Site	Baseline Evaluation Period		IF Evaluation Period			
	Start Date	End Date	Start Date	Date Paused for COVID-19	Date Reopened for COVID-19	End Date
MA Johns Hopkins ED	4/10/2017	4/9/2018	10/9/2018	N/A	N/A	10/8/2019
NY Mount Sinai ED/Beth Israel	7/6/2017	7/5/2018	1/4/2019	N/A	N/A	1/5/2020
OV University of Cincinnati ED	10/9/2017	10/8/2018	4/8/2019	03/13/2020	6/10/2020	7/6/2020
PNW Harborview Medical Center ED	1/2/2018	1/1/2019	7/2/2019	03/3/2020	6/6/2020	10/4/2020

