7.5.2 Sensitivity Analyses

To account for the pause in enrollment due to the COVID-19 pandemic, two separate sensitivity analyses will be conducted on the primary implementation and primary effectiveness outcomes.

First, the date sites closed enrollment due to the pandemic will be considered as the date closed for the study, whereby the analysis will be performed using only pre-COVID-19 data. This will show the “true” effect of the Implementation Facilitation on EDs with no effect of coronavirus. Secondly, the data entered after sites reopened their ED will be converted so that the pause in enrollment is removed. This will show whether the 3-month delay in recruitment due to COVID-19 had an impact on the primary implementation and primary effectiveness outcome analyses.

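### COVID-19 exposure lies only in the IF-period cells of two of the four EDs, so the site-by-period interaction for Day-30 engagement cannot separate a pandemic effect, if there was one, from a site difference

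*SAP*

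**What the plan says.** The Revised SAP (Analytic Model Adjustments) drops calendar time and makes site a fixed effect, which leaves a logistic model with site and evaluation period. Under Site Differences for Primary Effectiveness Outcome, it says that engagement rose at three sites, "however for one site there was a decrease". It continues: "To explore this further, a logistic regression model was fit assessing the site-by-evaluation period interaction". The interaction is reported as significant at p = 0.021, and future work is proposed, including "evaluation of differences in site characteristics that may explain the observed qualitative interaction". That section states no restriction of the data and does not mention COVID-19.

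SAP 3.3.6 records that "enrollment was paused due to the COVID-19 public health measures put into place at two sites" and gives each site's dates. SAP 7.5.2 says that "two separate sensitivity analyses will be conducted on the primary implementation and primary effectiveness outcomes". One analysis uses only pre-COVID data, treating the pause date as the closing date. The other removes the pause from the time scale. The shell for the effectiveness outcome (Table 29) has room for one overall coefficient and overall risk differences. It has no interaction and no site-specific effects.

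**The concern.** A site-by-period interaction asks whether the change from baseline to IF differs between sites. Exposure to the pandemic has the same structure: it is absent from every baseline cell, absent from two IF cells, and present to unequal degrees in the other two. With no time or pandemic term, the model has nowhere else to put a pandemic shift in engagement.

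The outcome definition offers a route for such a shift. Under SAP 7.3, a self-report without facility confirmation counts as not engaged. Under SAP 7.5.3, missing outcomes count as failures. Disrupted follow-up or facility contact could therefore lower the recorded rate even if treatment itself were unchanged. At stake is what can be said about where IF worked, not the primary implementation conclusion.

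**Working it through.** **1. The reported figure.** p = 0.021 cannot be reproduced, because the documents give no site-by-period counts. Four sites and two periods give a test on 3 degrees of freedom.

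**2. Exposure, from the SAP 3.3.6 dates.** Sites are labelled by the prefixes in that table.

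- Baseline: the last period ended on 1 January 2019, so no baseline patient was exposed.
- MA: IF enrolment ended on 8 October 2019; last Day 30 is 7 November 2019. Exposure 0%.
- NY: ended on 5 January 2020; last Day 30 is 4 February 2020, before the first pause on 3 March 2020. Exposure 0%.
- OV: 340 enrolment days before the pause (8 April 2019 to 12 March 2020) and 27 after reopening (10 June to 6 July 2020), total 367. Post-reopening share 27/367 = 7.4%. Patients enrolled from 12 February 2020 have Day 30 on or after the pause date; adding those 30 days gives 57/367 = 15.5%.
- PNW: 245 days before (2 July 2019 to 2 March 2020) and 121 after (6 June to 4 October 2020), total 366. Post-reopening share 121/366 = 33.1%. Adding the 30 days from 2 February 2020 gives 151/366 = 41.3%.

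**3. Apparent effect when the true IF effect is the same everywhere.** Inputs: about 120 patients per site-period (protocol 12.3), and engagement of 25% at baseline and 40% under IF (lower end of protocol Table 3). Applying the shares to 120 gives 9 and 40 exposed patients at OV and PNW (post-reopening) or 19 and 50 (Day-30 cut-off). The engagement rate in exposed patients is an assumption. At 20%:

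- PNW, 40 exposed: (80 × 0.40 + 40 × 0.20)/120 = 0.333, apparent effect +8.3 points.
- PNW, 50 exposed: (70 × 0.40 + 50 × 0.20)/120 = 0.317, +6.7 points.
- OV, 9 or 19 exposed: 0.385 or 0.368, +13.5 or +11.8 points.
- MA and NY: +15 points.

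The spurious shortfall at PNW is about 7 to 8 points.

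**4. Size of the interaction test.** For each site, L is the log odds ratio of IF against baseline (0.5 added to each cell) and w is the inverse of its variance. Q = Σ w(L − L̄)², with L̄ the weighted mean, is referred to chi-squared on 3 df. The table gives the rejection rate at 0.05 in 40,000 simulated trials with no true interaction.

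| IF rate, unexposed | Rate in exposed | Post-reopening exposure | Day-30 exposure |
|---|---|---|---|
| 40% | 40% | 4.7% | 4.8% |
| 40% | 30% | 5.6% | 6.1% |
| 40% | 20% | 8.7% | 11.6% |
| 40% | 10% | 15.0% | 22.4% |
| 40% | 60% | 8.5% | 10.8% |
| 50% | 20% | 14.0% | 19.4% |

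A p-value of 0.021 or less arises in 1.9% of trials with no pandemic effect, and in 3.9% or 5.7% with the 20-point fall from 40%. With exposed patients dropped, rejection is 4.5% to 4.9% in every scenario.

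**5. What a decrease at a late site would need.** With a true +15 points, the PNW mean falls below 25% only if engagement in 50 exposed patients is under (0.25 − 0.40 × 70/120)/(50/120) = 4%. With 40 exposed it cannot. With a true +5 points (IF rate 30%) and 15% in 50 exposed patients, the PNW mean change is (70 × 0.30 + 50 × 0.15)/120 − 0.25 = −1.3 points.

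**The case against.** A reader might infer that COVID-19 produced the significant interaction, or that it explains the site that went down. The documents support neither. They give no pandemic effect, sign or size. The decreasing site is not named; if it was MA or NY, exposure there was nil and the pandemic cannot explain that decrease. Step 5 shows that, at the planned effect, a pandemic-driven reversal in the mean needs an almost complete loss of engagement in exposed patients.

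A reader might also take the Revised SAP to conclude that site characteristics are the cause. Its wording is tentative: it offers them as one subject for future work. And use of all patients is inferred from the absence of a stated restriction; the text does not say so outright.

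The defence can add that SAP 7.5.2 already plans a pre-COVID analysis of this outcome, that the interaction is exploratory, and that a 10-point pandemic effect barely moves the test. All of that is fair. What remains is that the planned analysis stops at the overall effect. Its companion, which removes the pause, alters only the time variable and so does nothing in a model without time. No stated analysis examines the pandemic as a source of the heterogeneity that the Revised SAP reports.

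**Conclusion.** The point holds as a limit on interpretation. The dates establish that exposure is confined to two IF cells, and the stated model can express a pandemic effect only as a site difference. COVID-19 cannot be ruled out as a contributor to p = 0.021, but it is not shown to be one.

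On the plan's own rates (25% to 40%), the inflation is modest: about 6% for a 10-point fall and 9–12% for a 20-point fall. A clearly larger distortion needs most engagement among exposed patients to disappear, or a larger fall from a higher IF rate. A rise in engagement would inflate the test as well. These figures assume equal cells of 120, even enrolment over days and a common IF effect. SAP 11.0 reports very low recruitment at one site and fairly low recruitment at another, so the true cells were unequal. The primary implementation result is not affected.

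**What to change.** Extend the SAP 7.5.2 pre-COVID analysis to this model. Refit the interaction and report the four site-specific effects with intervals, beside the all-data result:

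- (a) excluding patients enrolled after the pause, which is the SAP 7.5.2 rule;
- (b) also excluding those whose Study Day 30 fell on or after their site's pause date, that is, enrolled from 12 February 2020 at OV and 2 February 2020 at PNW.

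An indicator for exposed patients in the all-data model is an alternative. Rule (b) suits a Day-30 outcome better, because rule (a) keeps 30 enrolment days at each late site whose outcome falls in the pause.

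Judge by how far the OV and PNW estimates move, not by whether significance persists. The subset loses power by itself: with a real interaction (+15 points at three sites, −5 at PNW) and no pandemic effect, power falls from about 64% to 50% under rule (b). Persistence would not prove a site-characteristics explanation either. State the pandemic as an alternative explanation alongside site characteristics.

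The cost is a rerun of an existing model on recorded enrolment dates. The downside is wider intervals at two sites: under rule (b), about 84% (310/367) and 59% (215/366) of their IF enrolment days remain.
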